### **7.5.1.9 Estimated blood sampling volumes and sampling priority list**

Applying the European Commission guidance (18), the study-related blood loss should not exceed 3% of the total blood volume during a period of 4 weeks and should not exceed 1% at any single time.

Local and/or regional guidelines regarding blood draw volumes may also apply.

Information of blood volumes per assessment type and sampling occasion are provided in a separate central laboratory manual. The total blood volume will not exceed 8 mL at a single time.

Blood sampling necessary for the clinical management of the patient will prevail over any study specific sampling.

Should the blood volume be restricted at any of the sampling time points, then the analyses should be prioritized in the following order:

1. Immunogenicity (ADA)
2. Coagulation
3. PK
4. Hematology
5. Blood chemistry
6. HS
7. Serum collection for future biomarker analyses

## **7.5.2 Demography**

The following demographic data are captured in the FIH study ([SOBI003-001](#)); date of birth (month and year), gestational age at birth, gender, ethnicity, race, country of residence and native language. In addition, information on the patient's sibling(s) is captured, including age and MPS IIIA diagnostic status (confirmed as non-affected/confirmed as affected/under current investigation). For sibling(s) with confirmed diagnosis, the sibling's age at diagnosis and genotype are also captured, when known.

Any changes to the patient's demographic data (i.e., country of residence) or information on the patient's siblings are recorded at Week 25 / Enrolment.

## **7.5.3 Efficacy assessments**

### **7.5.3.1 Neurocognition**

Neurocognition is assessed at Weeks 52 and 104, and during Early Termination, by use of the neurocognition domain of the BSID-III and/or the KABC-II Nonverbal Index (NVI).

The selection of neurocognitive assessment method is done at the baseline assessment of the FIH study ([SOBI003-001](#)) based on the algorithm presented in Table 11. The neurocognitive test(s) applied in the FIH study should also be used in the extension study.

**Table 11 Selection of neurocognitive assessment method**

Chronological age at the assessment time point	Development age-equivalence as established by VABS-II adaptive behavior composite	Neurocognitive test to apply
<42 months	Any age-equivalence	BSID-III
≥42 months	<36 months	BSID-III
≥42 months	36 to 42 months	BSID-III + KABC-II*
≥42 months	>42 months	KABC-II

\* The BSID-III should be administered first, and there should be at least 2 days until the KABC-II assessment in order to reduce KABC-II outcome bias of patient tiredness.

The neurocognitive developmental age (months) is derived on the basis of the BSID-III cognitive total raw score and BSID-III age-normative data.

The neurocognitive developmental age (months) is derived from the mean AEq scores on the NVI of the KABC-II, where an AEq scores is the average score for a particular age.

The Development Quotient (DQ) is obtained by dividing the neurocognitive developmental age with chronological age.

For patients completing an assessment of both BSID-III and KABC-II, the BSID-III score will be used as a basis for calculating the DQ of neurocognitive development at baseline. A calibration of overlapping AEq scores between BSID-III and KABC-II will be done to assess if a patient outgrows the BSID-III test during the duration of the study. If confirmed, assessments of KABC-II will form the basis for calculating DQ of neurocognitive development for remaining study assessments.

Neurocognition assessments are performed by child development specialists/psychologists with prior experience of MPS IIIA patients. Each patient should preferably have the same assessor throughout the study in order to reduce potential variability. When practically feasible, the aim should be to have the assessments performed in rested children early during the day, i.e., prior to 1 pm. The aim should also be to roughly keep the same assessment time point for an individual child, i.e., morning/afternoon.

To ensure that the BSID-III and KABC-II assessments are performed in accordance with the study instructions, completed assessment forms will be sent to a central reader (NeuroCog Trials) for data quality assurance, calculation of final scores and determination of Age Equivalence scores.

### 7.5.3.2 Adaptive behavior

Adaptive behavior is assessed at Weeks 52 and 104, and during Early Termination.

The patients' ability to cope with changes, to demonstrate independence and to learn new skills are assessed by use of the Parent/Caregiver Rating Form of the VABS-II. This measures five competence domains: communication, socialization, daily living skills, motor skills and an adaptive behavior composite of the first four domains.

The VABS-II is assessed by parent/caregiver. Every effort will be made to have the same parent/caregiver completing the form at each assessment time point.

The adaptive behavior age-equivalent score is determined as the mean of the subdomain age-equivalent scores including the communication, socialization, and daily living skills (thus excluding the motor skills domain).

Completed assessment forms will be sent to a central reader (NeuroCog Trials), for data quality assurance of completed assessment forms, calculation of final scores and determination of Age Equivalence scores, and data management.

### **7.5.3.3 Magnetic resonance imaging**

Brain and abdominal MRI are performed under general anesthesia at Weeks 52 and 104.

MRI scanning protocols including details on sequence parameters and scanning guidelines are provided to the clinical sites under the coordination of the central MRI reader. MRI field strength should be a minimum of 1.5, preferable, 3.0 tesla.

Preferably, the same MRI technician should perform all study related scans. The separate MRI assessment protocol provided prior to the study start should be followed for each scan. MRI data are sent to the central reader for quantitative analyses.

The brain MRI assessment protocol includes:

1. 3D T1-weighted MPRAGE (~6 min) for volumetric analysis
2. DTI and gre fieldmap (~10 min) for white matter analysis
3. 3D FLAIR and T2 (~8 min) for volumetric analysis
4. 4.SWI (~10 min) for iron content analysis

The abdominal MRI assessment protocol includes:

1. T1 3D VIBE (~2 min.)
2. T2 HASTE (~2 min.)

Liver/spleen volumes are evaluated by MRI using a standard MRI protocol.

### **7.5.3.4 Quality of life and caregiver burden**

The parent proxy-report format of the PedsQL questionnaire (Version 4.0) (29) will be used to assess the child's quality of life. The Family impact Module of the PedsQL (Version 2.0) will be used to assess the caregiver burden. The PedsQL will be completed at Baseline and at Weeks 52 and 104 and at early termination. Every effort should be made to have the same parent/caregiver responding to the PedsQL questions at each assessment time point.

The PedsQL version (i.e., infant/toddler/young children) will be selected on the basis of the chronological age of the patient.

### **7.5.3.5 Language**

Expressive and receptive language are assessed at Weeks 52 and 104, and during Early Termination, by the BSID-III language module and the VABS-II communication domain. In addition, written language is assessed by the VABS-II communication domain.

For those patients taking the KABC-II for cognitive assessment, the Expressive Vocabulary from the KABC-II is applied to assess language development.

### **7.5.3.6 Motor function**

Fine and gross motor skills are assessed at Weeks 52 and 104, and during Early Termination, by the BSID-III motor function module and the VABS-II motor skills domain.

### **7.5.3.7 Sleep pattern**

The patients' sleep pattern is evaluated using the CSHQ and by use of actigraphy.

Two additional items are added to the original CSHQ questionnaire to further characterize common MPS IIIA specific issues with sleep i.e. disruptive behavior at night and dangerous behavior at night. The CSHQ is completed by the primary caregiver prior to the infusions at Weeks 52 and 104. This CSHQ will capture the child's sleep habits during the past week. Every effort will be made to have the same caregiver completing the CSHQ at each assessment time point.

An actigraph will be applied to the non-dominant wrist and recordings will be made for 7 consecutive days and nights before the Weeks 52 and 104 assessments.

The wrist or ankle placement should be used consistently throughout the study period and be the same as used during the FIH (SOBI003-001) study. The device will be worn constantly during the recording periods only allowing removal for washing and bathing. The aim is to ensure that at least 5 days of evaluable recordings are obtained on each occasion. A daily wear time of 20 hours per day will be regarded as a compliant recording. The recording will be supported by an actigraph log. Recorded actigraph data will be evaluated using the accompanying software developed by the manufacturer. A subset of the actigraphy data is coded to be analyzed in a subsequent separate blinded analysis of the manually edited dataset.

The following parameters will be determined on the basis of recordings in the actigraph log:

- Bedtime (clock time child is put to bed)
- Wake time (clock time child is taken out of bed)
- Time in bed (time between Bedtime and Wake time)

The following variables are derived as obtained from the actigraph software:

- Sleep onset (clock time for first appearance of a predetermined number of consecutive min of sleep)
- Sleep offset (clock time for last of a predetermined number of consecutive min of sleep)
- Sleep period (time between sleep onset and sleep offset)
- Total sleep time (TST, duration of sleep in sleep period)
- Wake after sleep onset (WASO, number of minutes scored as wake during sleep period)

- Sleep efficiency (percentage sleep: TST/time in bed)
- Night waking frequency (number of night wakings)
- Night waking duration (sum of minutes scored as night waking)

24 h sleep duration (amount of sleep in a 24-hour period) Sleep onset latency is determined as Time between bedtime (as recorded on the actigraph log) and sleep onset (as captured by the actigraph software).

The Sadeh algorithm (28) is used for determining which epochs (1-minute recordings) are marked as “sleep” versus which are marked as “awake”. The Tudor-Locke method is applied to determine sleep periods, where 5 consecutive minutes of recorded “sleep” defines Sleep onset and where 10 consecutive minutes of “awake” time defines Sleep offset.

## **7.5.4 Safety assessments**

### **7.5.4.1 Adverse events**

#### **7.5.4.1.1 Definitions**

##### **Adverse event**

An AE is any untoward medical occurrence in a patient or trial subject administered a pharmaceutical product; the event does not necessarily have a causal relationship with the treatment or usage.

AEs include the following:

- Abnormal test findings, as specified below.
- Clinically significant signs and symptoms.
- Changes in physical examination findings.
- Unexpected progression/worsening of underlying disease.

In addition, signs and symptoms resulting from the following should also be handled according to the same principles as AEs:

- Overdose.
- Withdrawal of treatment.
- Interactions.
- Abuse.
- Misuse.

##### **Abnormal test findings**

An abnormal test finding, e.g. abnormal laboratory analysis results, vital signs or ECG, should be recorded as an AE in any of the following situations:

- The test is associated with accompanying symptoms. Note, that the symptom, not the test result, should be recorded as an AE.

- The test result leads to a medical/surgical intervention including withdrawal of IMP(s) or discontinuation from the study. Repeat/confirmatory testing is not considered a medical intervention.
- The investigator considers the test result to be clinically significant.

### **Preexisting conditions**

A preexisting condition (i.e., a disorder present before the AE reporting period started and noted on the pretreatment medical history/physical examination form of the FIH study ([SOBI003-001](#))) should not be reported as an AE unless the condition worsens or episodes increase in frequency during the AE reporting period.

### **Procedures**

Diagnostic and therapeutic non-invasive and invasive procedures, such as surgery, should not be reported as AE. However, the medical condition for which the procedure was performed should be reported if it meets the definition of an AE. For example, an acute appendicitis that begins during the AE reporting period should be reported as the AE and the resulting appendectomy entered in the comments section of the CRF.

### **Serious adverse event (SAE)**

An AE that meets one or more of the following criteria/outcomes is classified as serious:

- Results in death.
- Is life-threatening (i.e., at immediate risk of death).
- Requires in-patient hospitalization or prolongation of existing hospitalization.
- Results in persistent or significant disability/incapacity.
- Is a congenital anomaly/birth defect (i.e., in an offspring to the study subject).

Other medically important AE that may not result in death, be life threatening, or require hospitalization may be considered serious when, based upon appropriate medical judgment, they may jeopardize the patient or subject or may require medical or surgical intervention to prevent one of the outcomes listed above. Examples of such events are intensive treatment in an emergency room or at home for allergic bronchospasm, blood dyscrasias or convulsions that do not result in hospitalization or development of dependency or abuse.

Serious also includes any other event that the investigator or company judges to be serious. Any suspected transmission of an infectious agent via IMP shall also be considered serious.

### **Hospitalization**

Hospitalization includes transfers within a hospital (e.g. from the hospital ward to the intensive care unit) and also includes admissions less than 24 hours. The following situations are not considered hospitalizations (although other SAE criteria may still apply):

- Outpatient procedures / ambulatory care.
- Emergency department visits.

Hospitalization in the absence of an AE occurring during the study should not be considered an SAE. This includes:

- Hospitalization due to a pre-existing condition not associated with a worsening of the pre-existing condition.
- Protocol specified admission.
- Elective admission, e.g. due to cosmetic surgery.
- Pre-planned admission for a condition specified at Baseline for the patient.

#### **Treatment-emergent adverse event (TEAE)**

TEAE is any AE with onset or worsening reported from the time that the first dose of IMP is administered until completion of or early termination from the study.

##### 7.5.4.1.2 Adverse event reporting period

The period for recording AE, including SAEs, on the CRF begins Day 1 upon signing of the study ICF on Week 25 and ends at Day 8 of Week 104 (End of Study). This includes all events observed/diagnosed or reported since the last visit of the FIH study ([SOBI003-001](#)) (Week 24 / End of study).

In addition, SAEs should be reported, from the time the ICF is signed until 28 days past the last dose of IMP, unless the patient will continue SOBI003 treatment in a Sobi-sponsored extension study starting in direct connection to the study, collecting these events.

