Nonclinical safety assessments have been performed to support the SOBI003 development program. The nonclinical safety studies were performed in accordance to international standards for drug development and OECD Principles of GLP. A 3-month toxicity study was performed in MPS IIIA mice, a disease model to evaluate any potential interactions of the drug and the disease. A 1-month toxicity study in healthy non-human primates (cynomolgus monkey) was also performed. In addition, to support the clinical development in pediatric patients, juvenile rats were treated for one month from 10 days up to 5 weeks of age, which corresponds to a life-span in humans ranging from neonates up to the age of 6 years. Throughout the nonclinical safety program SOBI003 was administered by i.v. infusion every third day following pre-treatment with anti-histamine to appropriately resemble the clinical treatment regimen.

In the species tested, the treated animals did not show any signs of adverse effects. Thus, the safety evaluation of SOBI003 has shown that it is well-tolerated. In favor of SOBI003 treatment was also improvements in the disease state in MPS IIIA mice, such as lower incidences and/or severity of microscopic findings and with lower kidney, liver and spleen weights. However, the histopathological examinations revealed that the treatment of all three species at higher doses were associated with an accumulation of eosinophilic material in the cytoplasm of macrophages of various origin; liver, lymph nodes and the heart. The observations were clearly dose dependent and did not cause any detected harmful effects or other negative consequences to the animals. The observations were partially reversible after 4 weeks withdrawal of treatment. The anomalies were judged to be a result of a normal physiological function of tissue macrophages to scavenge proteins and the observed accumulation may be due to the high protein load. Thus, since these findings were not considered as adverse the NOAEL was set to the highest dose administered in the three species tested, i.e., 300 mg/kg in the mice and rats and 150 mg/kg in the cynomolgus monkeys.

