Potential delayed hypersensitivity reactions may occur outside the hospital setting (refer to Table 1) for minimum hospitalization periods during study participation). Parents/caregivers will be carefully informed of potential signs and symptoms of delayed hypersensitivity reactions and of the importance to seek immediate medical attention.

SOBI003 has the potential to become the first disease modifying therapy in patients with MPS IIIA. The disease-modifying effect of SOBI003 is believed to be most beneficial if treatment is started in very young patients since they have limited neuronal damage. SOBI003 could possibly stop, or reverse, the progress of the neuronal damage and the neurocognitive decline leading to a normal or a near normal neurocognitive development. In older patients, that have more pronounced neuronal damage, it is likely that already developed neuronal damage is not reversible. However, further disease progression might be prevented or at least slowed down.

The ultimate effect of the disease modifying effect would be to improve the cognition and thereby prolong life, minimize behavioral problems and sleep disturbances, and increase QoL including reduction of caregiver burden. The evaluation of the benefits of SOBI003 treatment in pediatric patients with MPS IIIA is based on the results in the SOBI003 non-clinical studies showing reduced levels of stored HS and its metabolites in brain and CSF, reduction of neuroinflammation in brain, reduction of lysosomal swelling and secondary storage products in brain as well as trends towards a beneficial effect on behavioral impairment. If translated to human these beneficial effects may reduce the devastating clinical manifestations of MPS IIIA.

Potential study procedural risks include the use of sedation/general anesthesia and use of a central venous access port. To minimize study related procedural risks, local hospital routines will be applied for the procedures. The selection of anesthetic method will be in accordance with local hospital routines and as judged by pediatric anesthesiologist with prior experience from MPS patients. The parents/caregivers will be trained in management of the port, in accordance with local hospital routines. This includes the actions to take in case an infection is suspected. The central venous access port is added as part of the preceding FIH study ([SOBI003-001](#)), but there may be occasions when a patient may need to replace an existing port.

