#### 7.5.1.6.2 Week 104, Day 2 to 7 Assessments

General anesthesia is applied in accordance with local routines at the study site. CSF sampling for PK, ADA, and HS assessments and MRI scanning of brain, liver and spleen are completed while the patient is anesthetized. The order of the procedures should preferably be as stated. Should this not be feasible for an individual patient, then effort should be made to have the assessments performed in the same order as they were performed in the FIH study ([SOBI003-001](#)). When separate consent for future research has been provided, CSF will also be collected for storage at the central laboratory.

At the time of CSF sample collection Day 2, a PK blood sample will also be collected. In case the time point for the CSF sample is deviating from the planned time point, the blood samples should be adjusted accordingly.

On Day 3, the VABS-II is assessed by parent/caregiver (refer to Section 7.5.3.2).

The parent/caregiver completes the PedsQL questionnaire, preferably during Day 4.

Based on the patient's developmental age, as determined by the VABS-II score, the BSID-III and/or KABC-II tests are conducted for assessment of neurocognition, language and motor function (see Sections 7.5.3.1, 7.5.3.2, and 7.5.3.6, respectively). If *only* BSID-III or *only* KABC-II is to be assessed, then this should be done on Day 7. If *both* BSID-III and KABC-II should be assessed, then the BSID-III should be administered on Day 4 or 5 and the KABC-II on Day 7.

On Day 7, a neurological and a complete physical examination are performed, an ECG is conducted and height, weight and head circumference are obtained. In addition, blood is collected on Day 8 (approximately 168h after start of SOBI003 infusion) for PK analyses as specified in Section 7.5.5.1.

The patient may be discharged from the hospital 1 hour or later after start of the infusion. The patient will then return to the hospital for study assessments as detailed in Schedule of Events (Table 7).

For patients that are permanently discontinuing SOBI003 treatment, serum samples for PK and ADA analyses should be obtained 30 to 40 days after last SOBI003 infusion. Patients with ADA-positive samples should continue to be followed in accordance with Sections 7.5.4.3 and 7.5.5.1.

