#### 7.5.1.8 Early withdrawal from treatment/study

If the patient is withdrawn from study treatment, the patient should be examined as soon as possible after making the withdrawal decision. AEs and use of concomitant medications are captured. Blood is collected for safety laboratory, HS, immunogenicity and PK assessments. Urine is collected for safety laboratory and HS assessments.

Vital signs are assessed, and a neurological and a physical examination are performed. An ECG is conducted, and height, weight and head circumference are obtained.

The VABS-II is assessed by parent/caregiver (refer to Section 7.5.3.2). The parent/caregiver completes the PedsQL questionnaire.

Based on the patient's developmental age, as determined by the VABS-II score, the BSID-III and/or KABC-II tests are conducted for assessment of neurocognition, language and motor function (see Sections 7.5.3.1, 7.5.3.2, and 7.5.3.6, respectively). If *both* BSID-III and KABC-II should be assessed, then the BSID-III should be administered 2 days prior to the completion of KABC-II.

When possible, study assessments (excluding SOBI003 infusion) of Weeks 38, 52, 78 and 104 should continue in accordance with the Schedule of Events. At minimum, the Early

Termination assessments should be repeated 30 to 40 days after the last SOBI003 administration. Patients with ADA-positive samples should continue to be followed in accordance with Sections 7.5.4.3 and 7.5.5.1.

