#### 7.5.4.1.5 Follow-up of unresolved adverse events

All AEs should be followed until they are resolved or the investigator assesses them as chronic or stable, or the patient's participation in the study ends, i.e., until Day 7 of Week 104 (End of Study). How to report changes in an ongoing AE during a patient's participation in the study is described in the CRF instructions.

In addition, all serious and non-serious AEs assessed by the investigator as related to SOBI003 should continue to be followed until they resolve or until the investigator assesses them as "chronic" or "stable", even after the patient's participation in the study is over.

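### For children who complete Week 104 and stop SOBI003, new non-serious AEs are not recorded after Day 8, and the AE and TEAE end dates conflict within and between the documents

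*Protocol*

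**What the plan says.** The primary endpoint is TEAEs and SAEs (protocol Section 6.1.1; SAP Section 3.5.1). The end of safety collection is set in several places.

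- **AE recording.** Protocol Section 7.5.4.1.2: the CRF recording period for AEs, SAEs included, "begins Day 1 upon signing of the study ICF on Week 25 and ends at Day 8 of Week 104 (End of Study".
- **SAE reporting.** The next paragraph of that section keeps SAEs reportable until 28 days after the last dose, unless the child moves directly into a sponsor extension study that collects them.
- **AE follow-up.** Protocol Section 7.5.4.1.5 follows AEs "until Day 7 of Week 104 (End of Study", although related AEs already on record are followed beyond the child's participation.
- **TEAE definition.** Protocol Section 7.5.4.1.1 counts events "from the time that the first dose of IMP is administered until completion of or early termination from the study". SAP Section 15.2 defines a TEAE by its start only and gives no end date.
- **Completers who stop.** Protocol Section 7.5.1.6.2: "serum samples for PK and ADA analyses should be obtained 30 to 40 days after last SOBI003 infusion". It lists no AE inquiry, vital signs or safety laboratory.
- **Early withdrawals.** Protocol Section 7.5.1.8 sets as a minimum that the Early "Termination assessments should be repeated 30 to 40 days after the last SOBI003 administration". Under Table 2 that set includes AEs, vital signs, physical and neurological examination, ECG, safety laboratory, ADA and PK.

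**The concern.** Both groups stop the same drug and both are contacted 30 to 40 days later, but only the withdrawn children are asked about AEs at that contact. The protocol gives no reason for the difference. How long non-serious AEs are observed after the last dose therefore depends on disposition, in a study whose primary objective is long-term safety.

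Protocol Section 7.5.4.3 plans to explore the effect of ADA on safety. An ADA result from the 30 to 40 day sample in a completer would have no non-serious AE or laboratory data from the same time beside it.

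The conflicting end dates are a separate matter. They leave open which late events are counted as treatment-emergent in the primary tables.

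**Working it through.** The plan states no figure to reproduce. The check is a day count on its stated windows.

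**1. End of AE recording.** Section 7.5.1.6.2 places Day 8 on the clock: "blood is collected on Day 8 (approximately 168h after start of SOBI003 infusion". Day 8 − Day 1 = 7 days, and 168 h / 24 = 7 days.

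**2. Windows after the last dose, for a completer who stops**

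| Item | Ends or occurs at |
|---|---|
| Safety laboratory (Tables 6 and 13) | before the Week 104 infusion; none afterwards |
| Vital signs (Tables 6 and 7) | within 1 hour after the Week 104 infusion |
| ECG, physical and neurological examination (Table 7) | Day 7 |
| AE follow-up (Section 7.5.4.1.5) | Day 7 |
| AE recording (Section 7.5.4.1.2) | Day 8 = 7 days after dose |
| SAE reporting (Section 7.5.4.1.2) | 28 days after dose |
| ADA and PK samples (Section 7.5.1.6.2) | 30 to 40 days after dose |

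**3. Gaps per child**

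- Non-serious AEs, to the end of SAE reporting: 28 − 7 = 21 days.
- Non-serious AEs, to the ADA/PK contact: 30 − 7 = 23 to 40 − 7 = 33 days.
- SAEs, to the ADA/PK contact: 30 − 28 = 2 to 40 − 28 = 12 days.

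**4. Size across the study.** Section 7.1 says only that continued access may be arranged, so the number who stop is between 0 and all of the 9 to 12 planned. If all stop, the total is between 9 × 23 = 207 and 12 × 33 = 396 patient-days, or 30 to 57 patient-weeks. If all continue in a sponsor study that collects these events, it is zero.

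**5. Share of follow-up.** With weekly dosing, all-AE observation after a late dose is 28 days for Week 101, 21 for Week 102, 14 for Week 103 and 7 for Week 104. Only the last 3 of 80 extension doses have less than 28 days. The 21-day gap is 21 / (560 + 21) = 3.6% of extension time, or 21 / (728 + 21) = 2.8% counted from the first dose in SOBI003-001.

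**6. Classification of an SAE after Day 8 and up to 28 days after the last dose.** Section 7.5.4.1.2 labels Day 8 as End of Study. If completion means that day, the event is not a TEAE under the protocol but is one under SAP Section 15.2. It enters the SAE table of SAP Section 15.2.2 either way. It enters the overview counts of serious TEAEs, and of TEAEs leading to death, only under the SAP definition. Section 7.5.4.1.2 also closes CRF recording of SAEs at Day 8 while keeping them reportable to 28 days, so it is unclear whether such an event reaches the clinical database.

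**7. Blood volume if the safety panel is added at 30 to 40 days.** Biochemistry 1.5 + hematology 0.5 + coagulation 1.7 = 3.7 mL (Table 13). Adding ADA 1.5 mL (Section 7.5.4.3) and PK 0.3 mL (Section 7.5.5.1) gives 5.5 mL, under the 8 mL single-draw limit of Section 7.5.1.9. The 1% limit in that section is met when total blood volume is at least 5.5 / 0.01 = 550 mL.

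**The case against.** The strongest reply is that serious late events are covered. SAEs are reportable to 28 days and tabulated in their own right. Deaths and events of major clinical concern that the investigator links to the study are reportable at any time (Section 7.5.4.1.4). A reader might infer that late reactions to the final doses are lost from the primary endpoint; the documents do not support that, because SAEs are a named part of it. This objection stands, and it limits the point to non-serious events and to SAEs after 28 days that fall outside Section 7.5.4.1.4.

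A reader might also infer that the plan itself describes harm arising after Day 8. It does not. Section 5.2 says "Potential delayed hypersensitivity reactions may occur outside the hospital setting" but gives no onset time, and routine discharge is possible 1 hour after an infusion. Section 5.1.3 says "The observations were partially reversible after 4 weeks withdrawal of treatment", but those were microscopic findings at higher doses in animals, judged not adverse.

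Nor would a positive late ADA result lack all safety data. AEs to Day 8, SAEs to 28 days, the Week 104 laboratory sample and a paired PK sample would exist. Only contemporaneous non-serious AE and laboratory data would be missing.

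Fuller follow-up of withdrawn children is defensible, since some stop because of an AE. The contrast is also less clean than it looks: the protocol TEAE period ends at early termination too, so AEs found at the 30 to 40 day repeat in a child withdrawn from the study may not be TEAEs either. That is a further reason to fix the definition.

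Finally, protocol Section 9.4.1 leaves analysis detail to the SAP, so the SAP's TEAE definition could be taken as the operative one. That would settle the counting, but an open-ended definition cannot count events that the CRF no longer records.

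**Conclusion.** The point holds in a limited form. For completers who permanently stop SOBI003, new non-serious AEs are not recorded after Day 8, although a contact is planned 23 to 33 days later. The loss is confined to those events and to SAEs after 28 days that do not meet Section 7.5.4.1.4. It concerns 0 to 12 children and a small share of total follow-up. With 9 to 12 children, however, one affected child is 8% to 11% of the study (1/12 to 1/9).

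The length of the window is a design choice that could be improved cheaply. The conflicts are errors: Day 7 against Day 8, and a TEAE period that closes in the protocol but not in the SAP.

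This rests on two assumptions: that study completion for a completer means Day 8 of Week 104, as Section 7.5.4.1.2 labels it, and that the 30 to 40 day contact collects only what Section 7.5.1.6.2 lists. How many non-serious events would occur in the gap cannot be estimated from the documents.

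**What to change.** 1. For completers who do not continue in a sponsor study that collects these events, record AEs and SAEs through the existing 30 to 40 day ADA/PK contact.
2. Use one TEAE end date in protocol Section 7.5.4.1.1 and SAP Section 15.2. It should cover that contact for completers and withdrawals alike, and say how to class later events in a child who is off treatment but still attending scheduled assessments.
3. Reconcile Day 7 in Section 7.5.4.1.5 with Day 8 in Section 7.5.4.1.2, and state that SAEs reported after Day 8 enter the clinical database.
4. Optionally, add the safety laboratory panel to the same draw: 5.5 mL in total, subject to the 1% limit for the individual child.

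The cost is wording in the protocol, SAP and CRF, and an AE inquiry at the contact. The plan says that samples should be obtained, not that a full site visit takes place, so the inquiry may need its own arrangement. Database lock could move by up to 33 / 7 = 4.7, about 5, weeks if the last patient does not roll over, or by less if lock already waits for the ADA/PK results.
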